8.2 Radiation Therapy Adverse Events

The descriptions and grading scales found in the revised NCI Common Terminology Criteria for Adverse Events (CTCAE), version 4 will be utilized for grading all adverse events. All appropriate treatment areas should have access to a copy of the CTCAE, v. 4. A copy of the CTCAE, v. 4 can be downloaded from the CTEP web site
 (██████████).

EVENTS EXPECTED

Erythema, dry desquamation, hyper or hypopigmentation are anticipated to occur commonly. Some patients may develop moist desquamation, which usually heals within 2-3 weeks. Mild swelling of the breast or mild breast pain are also likely side effects of treatment. It is not anticipated that treatment breaks should be needed, as severe acute toxicities are extremely rare.

Transient, persistent, and occasionally symptomatic seroma formation can occur and will be monitored for during treatment and at follow-up. Telangiectasia, and chronic changes in pigmentation can also commonly be seen, as can soft tissue fibrosis.

Infection is less likely, occurring in less than 10% of patients, generally following brachytherapy.

Skin or subcutaneous toxicity requiring surgery, pneumonitis, rib fractures, or any grade 3 or greater complications including pain are uncommon after ABPI, and are expected to occur in <10% of patients

Patients will also undergo venipuncture as part of the study. Risks of that procedure include hematoma, swelling, tenderness and inflammation at the site, persistent bleeding, vasovagal response, and rarely thrombosis and infection.

Method of detection, signs and symptoms, and method of treatment will be reported for all detected toxicities

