11.3 Cosmesis evaluation and Patient Reported Outcomes

11.31 Digital photographs should be performed according to the schedule outlined in section 4.0 and should include three poses: from the front with hands on hips and both lateral views. Recommended framing should go from the sternal notch to the umbilicus. If possible, patients should be photographed against a solid colored background.

11.32 The Harvard Cosmesis Scale will be used to score cosmesis according to the schedule outlined in section 4.0. The patients will be assessed as one of the following:

- Excellent: treated breast nearly identical to untreated breast
- Good: Treated breast slightly different than untreated (minimal but identifiable effects of the treated breast)

- Fair: Treated breast clearly different from untreated but not seriously distorted (significant radiation effects readily observable)
- Poor: Treated breast seriously distorted (severe sequelae of breast tissue secondary to radiation effects)

A modified version of the Harvard Cosmesis Scale will also be used for patient reported assessment of cosmesis.

11.33 The Breast Cancer Treatment Outcome Scale (BCTOS) is a self-report instrument that has high reliability and validity and will be used for evaluating patient-rated cosmesis according to the schedule outlined in section 4.0.

11.34 Patient-Reported Outcomes Version of the Common Terminology Criteria for Adverse Events (PRO-CTCAE) will be used for patient self-reporting of toxicities in the CTCAE.

11.35 Other Patient Reported Outcome questions (fatigue, pain, arm function etc.) included in the appendix.

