16.0 Statistical Considerations and Methodology

- 16.1 Overview: This is a single arm phase II study evaluating the rate of adverse cosmesis (defined as fair or poor cosmesis) at 3 years, compared to baseline, of 3 fraction accelerated APBI. For the analysis of the primary endpoint, patients will be pooled across the three treatment techniques (photon, proton, and brachytherapy) as was done in the the NSABP B-39/RTOG 0413 national multi-institutional randomized control trial comparing APBI with WBI. The three techniques utilized are recognized as standard options for the delivery of APBI, and there is no evidence that any technique is superior to any other with commonly used dose and fractionation regimens.⁴ The primary endpoint is the difference from baseline in the percentage of patients with adverse cosmesis (fair or poor cosmesis) at 3 years. The intent is to determine whether the difference of adverse cosmesis rate is acceptable. Of interest is whether the 3 fraction accelerated APBI results in an unacceptable increase in the adverse cosmesis rate at the end of 3 years, compared to baseline. If it does not, then the 3 fraction accelerated APBI will be recommended for further study. If the change in adverse cosmesis rate is found to be unacceptable, then the recommendation would be to do no further studies of the 3 fraction accelerated APBI. In addition to adverse cosmesis, this study will assess many additional secondary endpoints including IBTR (both invasive and non-invasive IBTRs will be considered), acute and late toxicity profile, quality of life measures, and translational studies.

16.2 **Primary Endpoint:** The primary endpoint is the percentage difference in patients with adverse cosmesis (fair or poor cosmesis) at 3 years compared to baseline. Cosmesis will be assessed by a trained nurse provider using the Harvard Cosmesis Scale.

All patients meeting the eligibility criteria who have signed a consent form, and begun treatment will be considered evaluable for the primary endpoint.

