16.4 Study Sample Size, Decision Rule, and Study Duration

16.41 *Sample size:* This study requires 153 evaluable women for the primary endpoint analysis. We anticipate accruing 15 additional patients to account for ineligibility, cancellation, major treatment violation, or other reasons. The maximum projected accrual is therefore 168 women, and we expect a maximum of 60 and a minimum of 40 women within each cohort (photon, proton, and brachytherapy).

16.42 *Study Decision Rule and Operating Characteristics:* Olivotto et al. previously reported interim cosmetic and toxicity results from a randomized trial comparing APBI using 3D-CRT versus WBI. In this study, the same 3DCRT dose and fractionation was used as in the previously discussed NSABP B-39/RTOG 0413 randomized controlled trial comparing 3DCRT or brachytherapy APBI with WBI. At 3 years, the percentage difference in patients with adverse cosmesis in the APBI arm compared to baseline by trained nursing assessment was 10.6%. The proposed analysis is to compute the percentage difference in patients with adverse cosmesis (fair or poor cosmesis) at 3 years compared to baseline. A one-sided 95% confidence interval (with the upper bound of the interval) was computed, by assuming the difference in adverse cosmesis rate at 3 years compared to baseline is 10%, and the distance from 10% to the upper bound of the CI is 4%. The decision rule would be of the following:

- If the upper bound of the one-sided CI for the difference of adverse cosmesis rate lies above 14%, then recommend no further investigation and conclude that there is no sufficient evidence to accept the adverse cosmesis rate of 3 fraction accelerated APBI.
- If the upper bound of the one-sided CI for the difference of adverse cosmesis rate lies below 14%, then recommend further investigation and conclude the increase in 3-year adverse cosmesis rate of 3 fraction accelerated APBI is potentially acceptable.

The study operating characteristics is determined as the chance of declaring that APBI warrants further study, assuming a true value for the difference in adverse cosmesis rate at 3 years compared to baseline for APBI. The table below shows the operating characteristics of this trial with 153 patients and the decision rule given above.

True increase in adverse cosmesis rate at 3 years compared to baseline	Probability of concluding PBI warrants further study
5%	98.4%
10%	72.8%
15%	48.6%
20%	29.8%

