16.44 Accrual time and Study duration: Since 10/1/2012 patients have been treated with brachytherapy APBI using an 8 or 10 fraction regimen and prospectively followed as part of a clinical registry at the Mayo Clinic in Rochester, MN. Patient interest in the procedure has steadily increased, and in the last 3 months, 13 patients have been treated (median 4.3 patients per month), all of whom would be eligible for this study. A similar to increased level of accrual of brachytherapy patients is anticipated during the course of this study as familiarity with this procedure amongst surgical and radiation oncology providers rises. With the addition of the photon APBI alternative for patients, we anticipate an accrual rate of 5 patients per month for the first year until the opening of

the Mayo proton facility, after which an accrual of 8 patients per month is anticipated. Therefore, the accrual period for this study is expected to be approximately 3 years. We plan to open this study at the Mayo Clinic in Scottsdale and Jacksonville which will further enhance accrual. Final analysis may begin approximately 5 years after the trial begins, i.e. as soon as the last patient registered has been observed for at least 24 months. A maximum of 60 patients and a minimum of 40 patients will be enrolled per treatment arm.

16.5 **Primary Analysis:** The primary analysis will be to estimate the percentage difference in patients with adverse cosmesis (fair or poor cosmesis) at 3 years compared to baseline. All patients meeting the eligibility criteria who have signed a consent form and started treatment will be in the primary analysis. The percentage difference in patients with adverse cosmesis will be estimated using a binomial estimator (number of women who had an adverse cosmesis event at 3 years minus number of women who had an adverse cosmesis event at baseline, and then divided by total number of women in the primary analysis) and a 95% exact binomial confidence interval. As mentioned above, the following decisions will be made based on the 95% CI:

- ***The upper bound of the 95% CI lies below 14%:*** APBI adverse cosmesis is acceptable.
- ***The upper bound of the 95% CI lies above 14%:*** No evidence to show that APBI adverse cosmesis is acceptable.

16.6 **Secondary Analyses**

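### A treated breast surgically corrected for radiation damage and then rated good or excellent at 3 years counts as non-adverse in the primary endpoint

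*Combined protocol and SAP*

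**What the plan says.** Section 16.2 sets the endpoint ("The primary endpoint is the percentage difference in patients with adverse cosmesis (fair or poor cosmesis) at 3 years compared to baseline") and names the rater and instrument: "Cosmesis will be assessed by a trained nurse provider using the Harvard Cosmesis Scale". Section 11.32 anchors that scale on a comparison of the two breasts; its top category reads "Excellent: treated breast nearly identical to untreated breast".

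Section 16.5 gives the numerator as "number of women who had an adverse cosmesis event at 3 years minus number of women who had an adverse cosmesis event at baseline", divided by the number of women in the analysis. On who is included, it says: "All patients meeting the eligibility criteria who have signed a consent form and started treatment will be in the primary analysis". The decision in 16.42 and 16.5 depends on whether the upper confidence bound for this net increase lies below 14%.

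Section 8.2 foresees surgery for radiation damage: "Skin or subcutaneous toxicity requiring surgery, pneumonitis, rib fractures, or any grade 3 or greater complications including pain are uncommon after ABPI". It puts that whole group of complications at under 10% of patients, and it also says that the method of treatment will be reported for every toxicity detected.

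Sections 11.32, 16.2 and 16.5 do not say how to score a woman whose treated breast was operated on for a radiation effect between radiotherapy and the 3-year rating.

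**The concern.** The trial exists to rule out an unacceptable rise in fair or poor cosmesis caused by the regimen. Damage bad enough to be repaired is part of that harm. If the repair succeeds, the nurse at 3 years sees a good breast and the estimator records no adverse outcome. The surgery does not take the woman out of the cosmesis assessments either: section 13.1 moves women to event monitoring for recurrence, and repair of a radiation effect is not recurrence. She stays in observation, in the denominator, and is rated as she then looks.

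Compared with counting her as adverse, this error has one direction. It lowers the measured increase and makes a favourable conclusion more likely. The other cosmesis measures do not correct it, because the patient's own rating and the panel's photographs at 3 years show the same repaired breast.

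**Working it through.** **Inputs.** Evaluable women: 153 (16.41). Assumed increase 10%, distance to the upper bound 4 percentage points, one-sided 95% confidence, pass line 14% (16.42). Exact binomial interval (16.5, which does not repeat whether it is one-sided). The net increase is treated as a single binomial proportion, as 16.5 does.

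**Step 1: the plan's sample size.** The usual precision formula is n = z² p(1 − p) / d². With z = 1.645, p = 0.10 and d = 0.04 it gives 152.19, rounded up to 153. This matches the plan. The two-sided version (z = 1.960) gives 216.08, or 217, and does not match, so the design was one-sided.

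**Step 2: the pass line in women.** The exact upper bound for x of n is the (1 − α) quantile of a Beta(x + 1, n − x) distribution, with n = 153.

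| Net adverse women | One-sided bound (α = 0.05) | Two-sided 95% upper bound (α = 0.025) |
|---|---|---|
| 12 (7.8%) | not needed | 13.30%, passes |
| 13 (8.5%) | not needed | 14.09%, fails |
| 14 (9.2%) | 13.93%, passes | 14.88%, fails |
| 15 (9.8%) | 14.69%, fails | 15.65%, fails |

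The trial passes with at most 14 net adverse women (one-sided) or at most 12 (two-sided). Under either reading, one woman reverses the decision at the line.

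**Step 3: effect of masking.** Let c be the share of all women whose damage was corrected and who then rate good or excellent. The documents give no value, so c is assumed to be 0, 1, 2, 3 or 5%. In 153 women these shares are 0, 1.5, 3.1, 4.6 and 7.7. With a true increase D, the measured increase has expectation D − c. The chance of passing is P(X ≤ 14) one-sided, or P(X ≤ 12) two-sided, with X binomial(153, D − c).

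| Masked share c (assumed) | True 14%, one-sided | True 14%, two-sided | True 15%, one-sided | True 15%, two-sided |
|---|---|---|---|---|
| 0% | 4.8% | 1.4% | 2.3% | 0.6% |
| 1% | 9.3% | 3.2% | 4.8% | 1.4% |
| 2% | 16.9% | 6.7% | 9.3% | 3.2% |
| 3% | 28.1% | 12.9% | 16.9% | 6.7% |
| 5% | 59.6% | 37.3% | 42.8% | 23.0% |

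These chances come from the decision rule as written. They will not agree with the operating-characteristics table in 16.42: that table gives 48.6% at a true 15% increase, where the one-sided exact rule gives 2.3%. That mismatch is a separate matter. The comparison here is between the rows of one calculation.

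**The case against.** **Silence is not a rule.** Nothing in the plan says that a rating is to be kept after surgery. That is true, but the endpoint, estimator and analysis set together have that effect for corrective surgery. Someone following 16.5 literally would count the repaired breast as good.

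**The damage is recorded elsewhere.** Section 8.2 requires the treatment of toxicities to be reported, 16.62 tabulates late events by maximum grade to 3 years, and 16.92 can suspend a modality for late grade 3 or higher events. Severe damage would not vanish from the trial. This stands. However, the acceptability conclusion in 16.5 rests on the cosmesis bound alone, so the record exists without reaching the primary result.

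**The size is unknown.** A reader might take the under-10% figure in 8.2 (at most 15 of 153 women) as the number at risk of masking. The documents do not support that. The figure pools surgery with pneumonitis, rib fracture and any complication of grade 3 or higher, so it is a loose ceiling and no estimate of corrective surgery. Nor does anything say that surgery restores a good rating; a repaired breast may still look clearly different and score adverse. A reader might also point to three masked women turning a true 17 of 153 (one-sided bound 16.20%, fail) into a reported 14 (13.93%, pass). The three are an assumption, and the example works only one-sided, since 14 of 153 already fails two-sided at 14.88%.

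**Surgery on the other breast.** A reader might infer that an operation for a new contralateral cancer makes the pair unequal and so scores as adverse. This is not established. The two adverse categories in 11.32 are tied to radiation effects ("Fair: Treated breast clearly different from untreated but not seriously distorted (significant radiation effects readily observable"; the poor category is worded in the same way), so a trained nurse need not give such a score.

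**Surgery for recurrence.** A reader might extend the point to this as well. Under 13.1 the woman moves to event monitoring, where the only form listed in 18.1 covers survival and disease status. Her 3-year rating is probably missing, not masked.

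**Comparability.** Recoding makes the endpoint a composite, while the 10.6% reference change quoted in 16.42 comes from another trial whose handling of operated breasts cannot be seen here. This is fair, and it is why the result on observed ratings should also be reported.

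**Conclusion.** The point holds for one group: women whose treated breast is surgically corrected for a radiation effect after radiotherapy and before the 3-year rating, and who are then rated good or excellent. For them the plan's own estimator records a non-adverse outcome. The error can only favour acceptability.

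Its size cannot be stated from the documents. On an assumed masked share of 0 to 5%, the chance of passing at a true 14% increase runs from 4.8% to 59.6% one-sided and from 1.4% to 37.3% two-sided. If no woman is corrected to a good rating, nothing changes; near the pass line, one such woman is enough. The figures assume 153 analysed women and a net increase that behaves as a single binomial proportion. The point does not extend to contralateral surgery or to surgery for recurrence.

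This is more than a missing detail, because the event is foreseen in 8.2 and the literal rule scores it in the favourable direction. It should be settled before 3-year ratings are examined.

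**What to change.** Add to 16.2 and 16.5:

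- A woman who, after completing radiotherapy and before her 3-year rating, has surgery on the treated breast to correct a radiation effect counts as adverse at 3 years. She is identified from the adverse-event treatment record that 8.2 already calls for.
- The same analysis on the observed 3-year ratings is reported as a sensitivity analysis.
- Women with contralateral or other breast surgery after radiotherapy are flagged, and the result is shown with and without them as a further sensitivity analysis.

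For that last group, replacing the 3-year score with the last rating before surgery is not advised. An early rating carried forward can miss later effects. A rule triggered by any surgery after baseline could also be set off by the lumpectomy or a re-excision if the baseline rating was made preoperatively. Counting only surgery after radiotherapy avoids the second problem.

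The cost is a few sentences of analysis text and a breast-surgery item (yes or no, with date) on the Patient Assessment form already listed in 18.1. The sample size stays at 153. The reported increase may be slightly less favourable, and a repaired breast that would have rated good without surgery will be counted as adverse; the observed-rating analysis shows how much that matters.

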1.1 Rationale for Accelerated Partial Breast Irradiation

The combination of breast conserving surgery and radiotherapy has been confirmed to provide equivalent disease-free and overall survival in multiple prospective randomized controlled trials with follow-up periods of over 20 years in early stage breast cancer.¹⁻³ Despite the cosmetic and potential emotional advantages of BCT (breast conserving therapy), many patients may choose mastectomy or decline radiation following lumpectomy due to the protracted nature of a conventional course of whole breast irradiation (WBI), which is delivered to the whole breast and frequently followed by a boost to the tumor bed, usually over 3-6.5 weeks.

The optimal volume of breast irradiation remains an area of ongoing study.⁴ Several lines of evidence suggest that WBI is unnecessary in a substantial number of patients with appropriately defined histological and clinical characteristics. For example, in a review of 217 mastectomy specimens, treated in Nijmegen, the Netherlands, residual disease was rarely identified more than 2 cm beyond the edge of the primary tumor unless an extensive intraductal component (EIC) was present.⁵ A pathologic analysis of reexcision specimens at William Beaumont Hospital demonstrated that in 90% of 134 patients with negative initial lumpectomy margins, any residual disease present was limited to <10mm from the edge of the original lumpectomy margin.⁶ Clinical validation of these histologic findings comes from analyses of patterns of failure after BCT which have shown that a majority of local recurrences in the first 5-10 years after BCT occur in close proximity of the original tumor, and the rate of recurrences outside of this area in the treated ipsilateral breast are similar to the rate of contralateral breast failures.⁷⁻¹⁰ With increasing follow-up, a larger proportion of recurrences are seen in other quadrants of the breast.⁷ Similar findings have also been seen in patients treated with lumpectomy without radiation, implying that an “in breast recurrence” may be due to growth of residual tumor cells left following the initial therapy (the target of adjuvant radiation), or the development of new primary tumors without relation to the initial breast cancer diagnosis.^{11,12} The impact of WBI in reducing local recurrence therefore appears to be primarily related to irradiation of the lumpectomy cavity and the immediately surrounding breast tissue.

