MIB requires a considerable amount of physician technical expertise and the majority of radiation oncologists who treat breast cancer routinely do not have training to perform these procedures. The MammoSite® (Hologic Inc., Marlborough, MA) breast brachytherapy applicator was designed to treat a similar volume of tissue around the lumpectomy cavity as MIB but with a single skin entry point, greater simplicity and less user-dependence.¹⁹ The American Society of Breast Surgeons (ASBS) MammoSite Breast Brachytherapy Registry Trial reported the outcomes of 1440 patients treated with this technique between 2002 and 2004 at 97 institutions. With a median follow-up for surviving patients of 53.7 months, the 5-year actuarial rate of ipsilateral breast tumor recurrence (IBTR) was 3.8% (3.86% for the 1249 patients with invasive breast cancer, 3.39% for the 194 patients with DCIS). In patients with invasive breast cancer, the 5-year actuarial rate of regional nodal failure was 0.84%. Negative estrogen receptor status was the only variable significantly associated with ipsilateral breast tumor recurrence (IBTR) and was limited to the development of breast failures several centimeters from the primary site and believed to be a new primary cancer. 90.6% of patients had a good or excellent cosmetic result at 5 years, and the only factor significantly associated with favorable cosmesis was increasing balloon-to-skin distance.²⁰

Multi-lumen balloon catheter devices (Mammosite® ML and Contura® [SenoRx, Irvine, CA]) and non-balloon bundled-catheter device (SAVI® [Strut Adjusted Volume Implant], Cianna Medical, Aliso, Viejo, CA]) were developed to provide greater conformality to the lumpectomy cavity while enabling better tailoring of dose around normal tissue structures like the skin, chest wall, and heart compared with single-lumen applicators. Fisher et al. reported their results of treatment of 117 patients with APBI brachytherapy between 2004 and 2010.²¹ Seventy-seven were treated with single-lumen balloon catheter Mammosite® and 40 with the SAVI® applicator, all to total doses of 34Gy in 10 fractions. Of the 40 patients treated with the SAVI® device, 12 had tumor bed-to-skin spacing of less than 7mm. None of these patients required device explantation, compared to 57% of patients treated with Mammosite when distances were <7mm. All 12 SAVI patients with minimal skin spacing had good or excellent cosmesis at short interval follow-up of 13 months thus far.²¹

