16.3 **Secondary Endpoints:** The secondary aims of this study are to characterize acute and late adverse events, assess patient self-reported and panel-reported cosmesis, IBTR rate, and quality of life as well as exploratory comparisons of cosmesis, toxicity, and IBTR rate between the 3 techniques. In addition, regional recurrence rates, distant recurrence rates, invasive disease-free survival, and overall survival will be estimated for each patient group treated with APBI. Blood will be collected for future studies in order to examine molecular and genomic predictors of adverse cosmesis and late toxicity.

The following definitions are used for the secondary endpoints of interest:

- *Acute adverse events* (up to 1 month post-RT): any adverse event, regardless of attribution, that occurs in the first month post-RT.
- *Late adverse events* (up to 3 years post XRT): any adverse event that occurred after the first month post-RT and up to 3 years post-RT.
- *Patient Reported Outcomes/Quality of life:* the Patient-Reported Outcomes Version of the Common Terminology Criteria for Adverse Events (PRO-CTCAE) will be used for patient self-reporting of toxicities in the CTCAE, along with other measures of fatigue, pain, and arm function listed in the appendix.
- *Patient self-reported cosmetic outcomes:* the patient self-reported outcome will be assessed using a modified Harvard Cosmesis Scale in the Breast Cancer Treatment Outcome Scale (BCTOS).
- *Panel assessed cosmetic outcome:* in addition to patient self-reported and physician reported outcomes, cosmesis will be assessed by a panel of breast cancer medical providers using digital photographs. The Panel will be blinded to treatment allocation.
- *IBTR:* this is defined as local recurrence at 3 years from trial registration as a first event. IBTR is defined as both invasive and non-invasive breast cancer involving the same breast parenchyma as the original tumor.
- *Regional recurrence:* invasive breast cancer in the axilla, regional lymph nodes, chest wall, and skin of the ipsilateral breast.
- *Distant recurrence:* metastatic cancer that has either been biopsy confirmed or clinically diagnosed as recurrent invasive breast cancer.

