16.61 *Acute adverse events (up to 90 days post-RT):* All patients who were registered to the study and started treatment will be included in the acute adverse event analysis. An acute adverse event is an AE, regardless of attribution, that occurs up to 90 days post-RT. The maximum grade for each type of acute AE will be recorded for each patient. Data will be summarized as frequencies and relative frequencies. Additionally, the relationship of the adverse event(s) to the study treatment will be taken into consideration.

16.62 *Late adverse events:* All patients who were registered to the study and started treatment will be included in the late adverse event analysis. A late adverse event is an AE, regardless of attribution, that occurs at least 90 days post-RT and up to 3 years post-RT. The maximum grade for each type of late AE will be recorded for each patient. Data will be summarized as frequencies and relative frequencies. Additionally, the relationship of the adverse event(s) to the study treatment will be taken into consideration. Prior APBI reports have suggested rates of grade 3 or 4 toxicity to be $\leq 10\%$.^{18,47,55,56}

16.63 *Quality of life:* The QOL measurements will be summarized at each time point as mean \pm SD and median (minimum value, maximum value). Changes in the QOL measurements from baseline will be determined at each follow-up measurement. These will be displayed as spaghetti plots. The assessment of the changes at each time point will be done with a paired t-test or Wilcoxon signed rank test, whichever is appropriate.

16.64 *Cosmesis*: The values of the cosmesis instruments (patient self-reported and panel-assessed) will be summarized with the frequencies of fair or poor cosmesis events at baseline and 3 years, and the difference at 3 years, as well as their relative exact binomial confidence intervals.

16.65 *IBTR incidence*: The IBTR cumulative incidence will be estimated using a competing risks method (Gooley et al.). The competing risks will be regional/distant breast cancer recurrence and death.

16.66 *Regional recurrence incidence*: The regional breast cancer recurrence cumulative incidence will be estimated using a competing risks method (Gooley et al.). The competing risks will be local/distant breast cancer recurrence and death.

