18.0 Records and Data Collection Procedures

18.1 Submission Timetable

Initial Material(s) -

CRF	Treatment (Compliance with Test Schedule Section 4.0)
Institutional Contacts	
Patient Eligibility	
Demographics	
On-Study	≤2 weeks after registration
Adverse Events- Baseline	
Specimen Submission: Blood (Baseline)	
Specimen Submission: Tissue (Baseline)*	*6 months from accrual
Patient Status: Baseline	
Patient Assessment	
Off Treatment	Submit ≤2 weeks after registration if withdrawal/refusal occurs prior to beginning protocol therapy

Test Schedule Material(s)

CRF	Post Radiation (cycle 2)	Observation ³ (subsequent cycles)
Radiation Treatment Form	X	
Patient Assessment	X	X
Specimen Submission: Blood (post rad tx)	X	

CRF	Post Radiation (cycle 2)	Observation ³ (subsequent cycles)
Adverse Events Solicited	X	X
Adverse Events Other	X ¹	X ¹
Off Treatment: Submit once per patient	X ¹	
Patient Status form	X	X
Adverse Events: Late		X ¹
Specimen Submission: Tissue (Recurrence)		X ¹
Consent Withdrawal form	X ¹	X ¹
Lost to Follow-up	X ¹	X ¹
Breast/Chest Wall Radiotherapy Questionnaire	X	X

1. When applicable
2. Survey will need to be entered manually if has not alternately been scanned or entered electronically
3. Observation (Active monitoring phase): 12 weeks (+/- 4 weeks), 12 months (+/- 30 days), annually for 5 years (+/-3 months). If a patient is still alive 5 years after registration, no further follow-up is required.

Follow-up Material(s)

CRF	Event Monitoring Phase ¹	
	12 months	Annually for 5 years ²
Patient Status: Survival and Disease Status Follow-Up/Event Monitoring	X	X

1. If a patient is still alive 5 years after registration, no further follow-up is required.
2. If patient has a recurrence prior to being off radiation therapy for 5 years, continue to follow yearly.

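### Late adverse events, and on one reading IBTR, stop at 3 years although the trial collects both to 5 years: add a 5-year report

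*Combined protocol and SAP*

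**What the plan says.** All references are to the combined protocol and SAP.

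- **IBTR definition (16.3):** "this is defined as local recurrence at 3 years from trial registration as a first event".
- **IBTR analysis (16.65):** "The IBTR cumulative incidence will be estimated using a competing risks method". No time point or horizon is given.
- **Late adverse events:** 16.3 counts "any adverse event that occurred after the first month post-RT and up to 3 years post-RT"; 16.62 counts an event "that occurs at least 90 days post-RT and up to 3 years post-RT". The two differ on when the window opens, but both close it at 3 years.
- **Invasive DFS (16.3) and DFS (16.68):** time from registration to first event, with no 3-year cap. Invasive IBTR is a component of invasive DFS.
- **Goals 2.21 and 2.22:** toxicity and local disease control, neither with a time limit.
- **Follow-up:** section 4.0, note 7, sets observation at 5 years in total. Footnote 3 to the observation column in 18.1 runs the visits "annually for 5 years (+/-3 months"). Patient assessment, solicited and late adverse-event forms and patient status are listed for that phase.
- **Reports:** 16.44 allows the final analysis once the last woman has 24 months of observation; 16.8 puts primary completion at 3 years. No 5-year report of IBTR or late toxicity is planned.

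**The concern.** Late toxicity and local control are the two stated secondary goals for which longer follow-up matters most. For toxicity, the plan collects events in years 4 and 5 and then excludes them by definition. For IBTR, the definition and the analysis section do not agree on whether years 4 and 5 count.

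This also leaves the endpoints inconsistent with one another. A first invasive IBTR in year 4 is an invasive-DFS event but not an IBTR under 16.3. A non-invasive one is neither, although it would count as recurrence in the DFS of 16.68.

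Finally, a 3-year IBTR cannot be set beside the recurrence rates that section 1.2 offers as context, because those are later. A lower figure at 3 years would be expected with no true difference.

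**Working it through.** **1. The plan's own figure.** The plan gives no sample size, event count or precision for IBTR or late toxicity. Its 153 evaluable women come from the cosmesis endpoint (16.42: difference 10%, distance 4%, one-sided 95%): n = 1.645² × 0.10 × 0.90 / 0.04² = 152.2, rounded up to 153. This reproduces. I use 153 below, not the 168 accrued, because the extra 15 allow for ineligibility, cancellation and violations.

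**2. Time points in section 1.2.** Nine studies give a local-recurrence rate at a named time.

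| Time | Studies |
|---|---|
| 4 years | RTOG 0319 (6%) |
| 5 years | Hungarian trial (3.4% APBI), RTOG 9517 (4%), MammoSite registry (3.8%), proton phase II (97% recurrence-free), TARGIT-A (3.3%), ELIOT (4.4%) |
| 7 years | Manchester trial (15%, ductal, tumor bed only), proton phase 1 trial (6%) |

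Six of nine are 5-year rates; none is a 3-year rate. For the registry the text reads "the 5-year actuarial rate of ipsilateral breast tumor recurrence (IBTR) was 3.8" percent.

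**3. Share of 5-year IBTRs that fall after year 3.** Assume a constant hazard, and ignore competing events and dropout. Then p3 = 1 − (1 − p5)^(3/5), and expected events are 153 × p. For p5 = 3.8%: p3 = 1 − 0.962^0.6 = 2.30%, so 3.5 events by year 3 against 5.8 by year 5.

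| 5-year rate (source) | 3-year rate | Events by 3 years | Events by 5 years | Share after year 3 |
|---|---|---|---|---|
| 1.5% (ELIOT women without unfavorable features) | 0.90% | 1.4 | 2.3 | 40% |
| 3.4% (Hungarian trial, APBI) | 2.05% | 3.1 | 5.2 | 40% |
| 3.8% (MammoSite registry) | 2.30% | 3.5 | 5.8 | 40% |
| 4.4% (ELIOT, intraoperative arm) | 2.66% | 4.1 | 6.7 | 40% |

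**4. Sensitivity to the hazard shape.** With a Weibull hazard and p5 = 3.8%, the share after year 3 is 31% at shape 0.75 (hazard falling), 53% at shape 1.5 and 64% at shape 2 (hazard rising).

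**5. Precision.** Clopper-Pearson 95% intervals: 4/153 = 2.6% (0.7% to 6.6%); 6/153 = 3.9% (1.5% to 8.3%). Both are wide and they overlap heavily.

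**6. Late toxicity.** The documents give no time-specific rate (the grade 3 or 4 figure of at most 10% in 16.62 has no time point), so the number of events lost cannot be calculated. What follows directly is that about two of the five scheduled years are outside the window.

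**7. When 5-year data would be complete.** At the rates in 16.44, accrual takes 12 + (168 − 60)/8 = 25.5 months, so the last woman reaches 5 years at month 25.5 + 60 = 85.5. With 3 years of accrual it is month 36 + 60 = 96. At month 60, when 16.44 expects the final analysis, essentially no one has 5 years.

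**The case against.** Three years is a coherent horizon for a phase II trial. It matches the primary endpoint, the 3-year RAPID cosmesis comparator and the primary completion date in 16.8. IBTR is descriptive, with no test or threshold against a published rate, and the expected difference is one or two events. All of this stands. It supports keeping the 3-year summaries, but it does not explain why years 4 and 5 are collected with no analysis defined for late toxicity.

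Four stronger readings are tempting, and the documents do not support them.

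- **Every IBTR after year 3 is certainly discarded.** A reader might infer this from 16.3. But 16.65 has no horizon and could be run on all follow-up, with 3 years as the reporting point. Later recurrences also count in DFS, and invasive ones in invasive DFS. What is established is a mismatch.
- **A 3-year rate would fall below every cited result.** It would not. Section 1.2 also reports 1% in the 199-patient series at a median of 60 months, one local recurrence among 100 women in the prone series at a median of 64 months, and 1.5% at 5 years in the ELIOT women without unfavorable features. The 2.3% in step 3 is above all three.
- **The background shows that a 3-year cut misses mainly failures elsewhere in the breast.** Section 1.1 does say "With increasing follow-up, a larger proportion of recurrences are seen in other quadrants of the breast". However, its 5-10 year statement is about location: most recurrences in that period lie near the original tumor. Years 3 and 5 are both inside or before it, so the text does not show a marked shift between them.
- **The trial's decision or its safety monitoring is compromised.** The go/no-go rule in 16.42 uses 3-year cosmesis only, and the late adverse-event suspension rule in 16.92 applies at any time after 6 months, with no 3-year cap.

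**Conclusion.** The point holds as an inexpensive improvement that should be made, not as a flaw in the primary analysis. The 3-year limit on late adverse events is unambiguous in two places. For IBTR, 16.3 and 16.65 must be reconciled, and 16.3 is out of step with the uncapped invasive DFS.

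For IBTR the size is about 40% of 5-year events under a constant hazard (31% to 64% over the Weibull shapes tried). In absolute terms that is about one event in 153 women at a 5-year rate of 1.5% and a little over two at 3.8%. This assumes that the cited rates carry over to this population and that competing events and dropout are negligible. The size for late toxicity cannot be derived from the documents. The comparability argument applies to local recurrence only.

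**What to change.** - **16.3, IBTR:** define it as time from registration to IBTR as first event, over all follow-up.
- **16.65:** report cumulative incidence at 3 and 5 years with 95% CIs, and descriptively by the two location classes in 11.221 (true recurrence/marginal miss, elsewhere).
- **16.3 and 16.62, late adverse events:** keep the 3-year summary and add one through 5 years, to the end of scheduled follow-up.
- **16.44:** add a data cut when the last woman reaches 5 years from registration.
- **Unchanged:** the 3-year primary endpoint and its timing. State that the IBTR and grade 3 conditions for pooling in 16.43 use the data of the primary analysis, so that the new definition does not reach it. A 5-year cosmesis summary in 16.64 is optional.

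No extra women, visits or forms are needed. The cost is the wording and one later report. Year 4-5 data may be incomplete: section 4.0, note 7, warns of this for women who cannot return on schedule, and in 18.1 the event-monitoring phase lists only the patient status form, so late toxicity is not captured there. The 5-year report should therefore give the number of women assessed each year. Its intervals will still be wide.
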